4.2.3.3 Rationale for Correlative Endpoints/Biomarker Research

Central hypothesis: Cutaneous squamous cell carcinoma (CSCC) is responsive to combination of PD-1 inhibition and radiation therapy.

To test our hypothesis correlatively we propose the following aims:

Aim 1. To correlate baseline PD-1 expression in the tumor with disease related outcomes.

Rationale: It is unknown whether patients with tumors that express higher levels of PD-1 preferentially respond compared to those that do not. As such, this will be systematically evaluated on all patients.

Research Plan: FFPE tissue blocks will be collected from patients and slides will be cut for subsequent biomarker staining. Analysis of PD-L1 expression will be performed by immunohistochemical staining using the Merck assay. Either complete circumferential or partial linear plasma membrane staining will constitute positive PD-L1 staining. A cut-off of $\geq 5\%$ tumor cell membrane staining will be reported as positive.

Aim 2. To define response to radiation/PD-1 inhibition based on tumor microenvironment and peripheral blood alterations in patients with CSCC.

Rationale: Many solid tumors do respond to checkpoint inhibitors. Little is known in regards to CSCC patients who will or will not respond to the proposed treatment regimen of post-operative radiation and anti-PD-1 therapy.

Research Plan: Prospectively we will stratify study patients into two groups: those that do, or do not respond to the proposed therapy based on historical published data from our institution. The following are the proposed assays for evaluation.

A. Peripheral Blood Lymphocytes

Flow cytometry: Peripheral blood samples drawn from patients pretreatment and at specified times post treatment will be isolated by centrifugation. Surface biomarker expression will be assessed by FACS similar to the analysis of tumor-resident lymphocytes. Staining will evaluate CD3, CD4, CD8 expression as well as cytotoxic markers (perforin, FasL, Granzyme A&B, markers of dysfunction/exhaustion (PD-1, TIM-3, Lag-3), and markers characteristic of regulatory cells (Foxp3, CD25, GITR, CD27, CD28) and markers for myeloid derived suppressor cells. Finally, we will assess TCR clonal diversity using PCR methods.

B. Tissue

Patients for whom fresh tissue is available (e.g. if they consented to other tissue banking IRB approved protocols such as IRB 3164 or 15-1580) or for whom FFPE is available, may have some or all of the following additional correlative studies performed, depending on tissue availability.

These include:

Immunohistochemistry: Tumor tissues will be stained and evaluated for indicators of inflammation including the relative degree of lymphocyte infiltration and characterization of immune populations via expression of CD3, CD4, and CD8, as well as the expression of various regulatory-associated markers including PD-1, PDL-1, and galectin-9.

Flow cytometry: tumor tissue will be disassociated by digestion with collagenase/hyaluronidase, prior to FACS analysis of immune population phenotype including CD3, CD4, CD8, and the following cytotoxic markers: perforin, FasL, Granzyme. Studies will also evaluate markers of dysfunction/exhaustion including PD-1, TIM-3, Lag-3, TIGIT and markers associated with regulatory cells/suppression including Foxp3, GITR, CD25, CD27, and CD28 and markers for myeloid derived suppressor cells. Finally, we will assess TCR clonal diversity using PCR methods.

Cytotoxicity assays: Tumor resident CD3+CD8+ T cells will be purified by FACS sorting and functionally evaluated for recognition of autologous SCCA and/or general functional ability. Readouts will include proliferation (CFSE dilution, 3-H thymidine incorporation), cytotoxicity (51-Cr release, CD107a staining), and production of interferon gamma and IL-2.

Gene expression analysis: Tumor tissue specimens will be checked by a pathologist to ensure that each contains at least 60% tumor content. Total RNA will then be isolated from 30 to 60 mg of snap-frozen tissue followed by purification of mRNA. Isolated mRNA will then be used to construct a library using the non-stranded TruSeqs protocol, which will then be subjected to high-throughput shotgun sequencing using the Illumina HiSeq 2500 platform by the Case Western Reserve University Genomics Core. Data analysis of transcription profiles will be done in association with the CWRU Genomics Core and correlated with treatment outcome and overall survival data.

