3.2 Secondary Objective(s) & Hypothesis(es)

(1) **Objective:**

- 5) To evaluate the relationship of baseline PD-L1 expression by tumor and tumor-infiltrating lymphocytes (TILs) to preliminary efficacy .
- 6) To phenotype tumor infiltrating lymphocytes and peripheral blood lymphocytes (PBLs), and investigate tumor suppressor populations including Tregs, MDSCs and CD8 suppressor

cells and assess ex vivo for effector function by cytokine production and cytotoxicity assays as well as suppressor function in assays with autologous PBLs.

- 7) For those participants for whom tumor tissue is available, we will evaluate the tumor microenvironment (TME), and immune markers at the invasive margin of the tumor, including CD8, PD-1, PD-L1, TIM-3, galectin-9 or HMGB-1, BTLA and HVEM, as well as Lag-3, CTLA-4 and others.
- 8) If sufficient tumor is available, we will also evaluate the genomic and/or transcriptomic profile of a subset of tumors using RNA-seq /Whole Transcriptome Shotgun Sequencing

Hypotheses:

- 1) Baseline PD-L1 expression will not be associated with 1yr PFS.
- 2) Peripheral immune profiles on PBMC will dynamically change from baseline through treatment and after completion of therapy and correlate with 1yr PFS.
- 3) Changes in the TME at the marginal edge of the tumor will correlate with 1yr PFS and be marker dependent.
- 4) Baseline genomic/proteomic tumor profiles will correlate with 1yr PFS

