5.0 METHODOLOGY

5.1 Entry Criteria

5.1.1 Subject Inclusion Criteria

In order to be eligible for participation in this trial, the subject must:

- 1) Histologic diagnosis of cutaneous squamous cell carcinoma of the head and neck that has been resected with no evidence of gross residual disease (margin positivity is acceptable).
- 2) Patients must have undergone resection of the disease and demonstrate high risk pathologic features including:

- Invasion of the axial skeleton or skull base or skull base foramina
 - Node positive disease
 - Tumor greater than 2cm with any 1 additional feature, including:
 - Recurrent Disease
 - Perineural invasion
 - Lymphovascular space invasion
 - Poorly differentiated histology
 - Positive Margins
 - Satellitosis or in-transit metastases
- Note: Not all patients with tumors >2cm with one additional risk factor may be ideal candidates for this study, such as patients with only focal perineural invasion without other adverse features. Clinical judgment should be used by the investigator in carefully selecting patients believed to be at significant risk of recurrence with radiation alone.
- 3) Patients are required to have CT neck and chest or PET/CT and have no documented evidence of distant metastases
 - 4) Patients must not have a history of the following immunosuppressive conditions: bone marrow transplantation and/or organ transplants and/or chronic rheumatic conditions that require active immunosuppressive therapy. Patients with a history of chronic lymphoid or leukemic malignancies which are not under active therapy (no active therapy within the last 3 months) will be eligible. Patients with chronic lymphoid or leukemic malignancies are eligible with or without active disease as long as they have not had treatment within the past three months.
 - 5) Patients may not have had prior therapy with a checkpoint inhibitor (e.g. anti-CTLA-4, anti-PD-1 or anti-PD-L1 therapy);
 - 6) Patients may not have had prior radiotherapy (>30Gy) to the area requiring treatment that would result in any overlap of tissue in both fields

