6.0 TRIAL FLOW CHART

6.1 Study Flow Chart

		Study Treatment (weeks)										Post- tx	Long term f/u	
		1	2	3	4	5	6	7	10	13	16			20 ^f
Medical History, PE, Vital Signs	x	x	x	x	x	x	x	x	x	x	x	x	x	x
Height	x													
Weight	x	x	x	x	x	x	x	x	x	x	x	x	x	x
ECOG PS	x	x	x	x	x	x	x	x	x	x	x	x	x	x
CBC with Differential	x	x			x			x	x	x	x	x	x	x
Complete metabolic panel	x	x			x			x	x	x	x	x	x	x
Concomitant meds	x	x			x			x	x	x	x	x	x	x
Pregnancy test ^b	x													
TSH	x	x			x			x	x	x	x	x	x	x
Immune Status History	x													

CT neck and chest (with contrast if possible) ^c (CT Chest preferred, CXR acceptable)	x												x	x
PET/CT and/or MRI ^c (optional)	x													
Dental evaluation ^d	x													
Pembrolizumab		x			x			x	x	x	x			
IMRT			x	x	x	x	x	x						
Adverse event evaluation		x			x			x	x	x	x		x	
Correlatives: submission of tumor tissue ^e	x													
Correlatives: blood ^e	x							x					x	x (52 wks)

a. Pre-treatment evaluations will be performed within 4 weeks prior to registration, unless otherwise specified. This excludes imaging which will be eligible within 12 weeks of registration on study.

b. For women of childbearing potential, pregnancy test must be completed within 2 weeks of beginning treatment.

- c. CT neck and chest CT will be acceptable if done within 12 weeks of trial registration. PET/CT is optional and only recommended if there is concern for gross

- residual disease. MRI brain and/or orbits may be important for tumors near the skull base, especially those with perineural invasion. In these cases, MRI is recommended to be obtained at baseline, at wk 20 follow up, and at later follow up visits as clinically indicated. While the routine surveillance **images** are scheduled for weeks 20, 32 and 52, changes in patient symptoms or persistent symptoms may prompt the clinician to order a CT at any time, as per standard practice.
- d. Dental evaluation is recommended for those who will receive significant (>45Gy) dose of radiation to the mandible. However, it is not required.
 - e. Baseline tumor tissue will be sent to Merck for PD-1 testing. Blood will be collected at designated times (+/- 4 weeks to accommodate patient preference, transportation needs and scheduling needs around coordination of appointments) and sent to the [name] lab. Additional study of tumor tissue (fresh and/or FFPE) may be done if the patient has consented to other tissue banking protocols.

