7.1.2.5 Tumor Imaging and Assessment of Disease

As this is an adjuvant trial, there will be no anticipated measureable disease to record. RECIST and other such response criteria do not apply. However, there will be baseline imaging and surveillance imaging to evaluate for locoregional and distant recurrence as specified in the

Trial Flow Chart (section 6.0). In the event of clinical or radiographic recurrence of disease, biopsy to confirm recurrent disease is strongly recommended.

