8.3 Statistical Analysis Plan

DLT will be estimated using an exact 95% confidence interval. If 11 or more patients experience DLT the regimen will be considered too toxic. One-year PFS will be estimated using the Kaplan-Meier method and a 95% confidence interval constructed using Greenwood's method. One year PFS outcomes will be assessed overall and also separately for immunocompetent patients vs. immunosuppressed patients (e.g. CLL). These outcomes will be compared to our historical dataset for both subsets respectively. Adverse events will be tabulated by category and grade. The rates of

adverse events will be estimated using an exact 95% confidence. The relationship between 1yr PFS and baseline PD-L1 expression will be assessed using logistic regression. Immunoprofiles in peripheral blood in serial samples will be tested using random effects ANOVA. Bioinformatic analysis will be applied to all genomic and transcriptomic data.

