Appendix 10.10 – Tissue and Blood processing for correlative science

Study #1: Specimen Collection for PD-L1 Expression			

 All patients will have slides cut from FFPE tissue blocks for analysis of PD-L1 expression by IHC staining FFPE tissue will be obtained from the Tissue Procurement and/or pathology department (CCF) or Biorepository and/or pathology department (UH) and assigned a unique identification number. All other PHI will be redacted from the pathology report. Five slides will be cut from each FFPE block for PD-L1 and H&E staining. 
 One slide each for H&E, PD-L1, and Isotype and two for repeat staining if needed Results: QualTek Molecular Laboratories Clinical Laboratories will report to Merck and study investigators. Residual Material: FFPE specimens will be retained by Cleveland Clinic and University Hospitals in anatomic pathology per their routine, and made available for future use as indicated. 
Study #1 Specimens shipped to:
 
QualTekMolecularLaboratories MISP Receiving [name] [name] [contact] [contact] [contact]
			
Specimen Type	Collection Time Points	Collection Information and Requirements	Shipping
Five slides from primary tumor FFPE blocks	Baseline Tumor specimen	Sections will be 4 micron thickness onto Fisher ProbeOn Plus Slides, Cat Number 22-230-900. Tissue sections must be placed on the painted/textured side of the slide.	Slides shipped cold (2-8°C) and in the dark using QualTek-supplied packing materials.

Study #2: Blood Collection for Immune Biomarker Analysis

- All patients will have blood collected at specific time points (pre-treatment and weeks 7, 20, and 52). +/- 4 weeks is allowed on follow up visits.
- At each time point, up to 50cc of blood will be collected and processed by research laboratory personnel ([name], PI) to isolate lymphocytes and freeze for further analysis.
- Specimens will be assigned the same unique identification number used for Study #1 and any other personal health information (PHI) will be redacted from the pathology report.
- Results: Research laboratory personnel will report to Merck and study investigators.
- Residual Material: cryopreserved specimens will be retained by the research laboratory until the study conclusion.

For CC: Samples will typically be collected by CRA. [name] lab will then be contacted as follows:

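### The blood correlatives split patients by an undefined response, the stated ANOVA has no outcome term, and relating week-20 and week-52 samples to 1-year PFS is liable to bias

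*Combined protocol and SAP*

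**What the plan says.** **Grouping.** Section 4.2.3.3, Aim 2: "Prospectively we will stratify study patients into two groups: those that do, or do not respond to the proposed therapy". The stated basis is historical institutional data. No rule, cut-off or time point follows, and both the blood and the tissue assays are listed under this aim.

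**Response.** Section 5.1.1 requires resection without gross residual disease. Section 7.1.2.5 says "RECIST and other such response criteria do not apply", and provides surveillance imaging for recurrence.

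**Hypothesis.** Section 3.2, hypothesis 2: "Peripheral immune profiles on PBMC will dynamically change from baseline through treatment and after completion of therapy and correlate with 1yr PFS".

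**Analysis.** Section 8.3: "Immunoprofiles in peripheral blood in serial samples will be tested using random effects ANOVA". That section names a model for 1-year PFS (logistic regression) only for baseline PD-L1.

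**Sampling.** Appendix 10.10, Study #2: "All patients will have blood collected at specific time points (pre-treatment and weeks 7, 20, and 52"; it allows 4 weeks either side for follow-up visits. Footnote e to the Section 6.1 flow chart says "Blood will be collected at designated times (+/- 4 weeks to accommodate patient preference" and does not limit this to follow-up visits.

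**After progression.** Section 5.9 requires discontinuation from the trial for confirmed radiographic progression. Section 7.1.1.7 moves patients who start new anti-cancer therapy into survival follow-up. Section 7.1.5.3 mentions only overall survival follow-up after recurrence, and follow-up blood only where applicable. Section 7.1.3.1 asks for the applicable final-visit activities at discontinuation.

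**The concern.** Two outcomes are attached to the same samples, and one of them cannot be constructed in an adjuvant trial. The analyst would have to invent the split, possibly after seeing the data. The one model stated for the serial samples does not mention outcome at all, so half of hypothesis 2 has no stated test.

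Timing adds a second problem. If patients are classified by what happens up to week 52 and then compared on week-20 and week-52 blood, some samples are taken after the event that defines the group, or are absent because of it. A difference could then be a consequence of recurrence, or of who was still being sampled, and not a marker of later outcome. A listed secondary hypothesis would be left without a clear answer. The tissue assays share only the first problem, because tissue is taken at baseline.

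**Working it through.** **1. The plan's own figures.** None is given for this analysis. The design figures concern DLT. With 34 evaluable patients and a limit of 11, P(X ≥ 11 | 0.20) = 0.062 and P(X ≥ 11 | 0.40) = 0.862, which agree with the 6% and 86% in Section 8.2. They supply n = 34 and nothing more here.

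**2. Outcome.** Aim 2 uses response, Section 7.1.2.5 rules out response criteria, and Section 3.2 uses 1-year PFS. Section 8.1 defines PFS (progression or death from any cause, from treatment initiation), so PFS is the assessable one.

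**3. What a time-only ANOVA can see.** Section 8.3 lists no model terms, so this step assumes a time effect only. Simulation: n = 34, 3,000 runs, draws at weeks 0, 7, 20 and 52, none missing. Assumed: true baseline level SD 1; individual slope with mean 0 and SD 0.7 per 52 weeks; measurement error SD 0.5; log hazard ratio −1 per SD of baseline level; 1-year PFS at the mean marker value of 60, 70 or 80%.
- Test of change over time: rejects in 5.0, 5.4 and 5.3% of runs, its null level.
- Comparison of baseline values between those with and without an event by week 52: rejects in 81.0, 74.5 and 63.4%.

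The association is present in every run, and the time-only test does not respond to it.

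**4. Who is event-free at each draw.** The documents give no 1-year PFS, so S is assumed over 60–90% with constant hazard. Events by week 52 = 34(1 − S). Of those patients, the number still event-free at week t = 34(S^(t/52) − S). Share of events before week 20 = (1 − S^(20/52))/(1 − S).

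| S | Events by wk 52 | Event-free at wk 7 | At wk 20 | At wk 52 | Share before wk 20 |
|---|---|---|---|---|---|
| 60% | 13.6 | 11.3 | 7.5 | 0 | 45% |
| 70% | 10.2 | 8.6 | 5.8 | 0 | 43% |
| 80% | 6.8 | 5.8 | 4.0 | 0 | 41% |
| 90% | 3.4 | 2.9 | 2.0 | 0 | 40% |

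The week-52 draw may fall at weeks 48–56. Even at week 48 only 0.2–0.8 of these patients are still event-free, so that draw coincides with the endpoint.

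**5. Does selective sampling distort the result?** Same simulation, with only patients event-free at week 52 sampled then. When the slope drives the hazard (log hazard ratio −1 per unit of slope), the mean week-52 change is +0.24, +0.18 and +0.12 baseline SD for S = 60, 70 and 80%, against a true value of 0. When only the baseline level drives the hazard, it is 0.00. These are simple means, not fits of a random effects model. Bias is possible, not inevitable.

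**6. The week-7 window.** Under footnote e, 7 ± 4 gives weeks 3–11. By Table 2 (Section 5.2), week 3 follows one scheduled pembrolizumab dose, with IMRT under way. Week 11 follows four (weeks 1, 4, 7, 10), with IMRT scheduled to be complete. Appendix 10.10 gives no window for week 7.

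**7. Precision.** Detectable difference between outcome groups = (1.96 + 0.84)√(1/n₁ + 1/n₂), two-sided 5%, 80% power. With all 34 patients it is 0.98–1.60 SD for S = 60–90%. With only the eventual events still event-free at week 20, it is 1.19–2.02 SD.

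**The case against.** Several stronger readings are tempting, and the documents do not support them.

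- *No assessable outcome exists.* It does: Section 3.2 names 1-year PFS and Section 7.1.2.5 provides imaging for recurrence. The fault is an undefined term that conflicts with a defined one.
- *The ANOVA cannot test the association.* A random effects ANOVA could carry a group-by-time term, and Aim 2 read with Section 8.3 does not exclude one. But none is written, and the group it would need is the undefined one. The simulation in step 3 rests on a time-only reading.
- *The association is biased.* Comparing baseline or week-7 values between groups defined by later outcome is not biased in itself, and step 5 gives zero distortion in one case. Liable to bias is as far as one can go. Section 3.2 also says correlate, not predict.
- *Blood sampling stops at progression.* No section says so. Appendix 10.10 says all patients, and Section 7.1.3.1 may yield a sample at discontinuation. That sample's timing would then be set by the outcome, so the difficulty changes form but remains.

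The counts are also open to challenge. Routine surveillance imaging starts at week 20, so recorded recurrences should cluster at weeks 20, 32 and 52, and constant hazard probably places too many events before week 20. This stands. It also means that a recurrence may be found at the visit of the week-20 draw, so that sample may reflect recurrence already present.

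Finally, Section 1.0 calls these objectives correlative, and the decision to proceed in Section 2.1 rests on DLT and 1-year PFS. That limits the weight of the point and does not remove it.

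**Conclusion.** Two parts hold on the text alone. Response is undefined and conflicts with the PFS outcome in Section 3.2, and no outcome term is stated for serial blood, so the correlation half of hypothesis 2 has no stated test.

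A third part holds as a risk. Relating later samples to 1-year PFS is liable to bias through samples that are missing by outcome or taken at or after recurrence. The risk is strong at week 52, moderate at week 20 and minor at week 7. Its size and direction depend on an unknown relation between marker and progression.

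The event counts (about 3–14 by week 52) rest on an assumed 1-year PFS of 60–90%, constant hazard and 34 patients. With so few events, any association analysis is exploratory. The primary endpoints are unaffected.

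**What to change.** In Sections 4.2.3.3 and 8.3:

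1. Replace the responder split with PFS (progression or death).
2. Relate baseline markers to PFS. Relate the change from baseline to week 7 (supportive: week 20) to PFS after that landmark, among patients event-free at it, for example by Cox regression. A mixed model with an outcome-by-time term, or a joint model, would be alternatives; what matters is to name one in advance. State how a recurrence found on the week-20 scan is classed.
3. Keep the random effects ANOVA, including week-52 samples, only to describe change over time, and report how many patients sampled at each draw were event-free.
4. State whether blood is drawn after progression and how missing samples are handled.
5. Reconcile footnote e of Section 6.1 with Appendix 10.10 for the week-7 draw, and analyse by actual sample date.
6. Label the association analysis exploratory.

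The cost is SAP wording, with no new patients or visits. The landmark sets lose early events: under constant hazard about 14–17% of events at week 7, from (1 − S^(7/52))/(1 − S), and about 40–45% at week 20. Precision is low in either set.

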5.0 METHODOLOGY

5.1 Entry Criteria

5.1.1 Subject Inclusion Criteria

In order to be eligible for participation in this trial, the subject must:

- 1) Histologic diagnosis of cutaneous squamous cell carcinoma of the head and neck that has been resected with no evidence of gross residual disease (margin positivity is acceptable).
- 2) Patients must have undergone resection of the disease and demonstrate high risk pathologic features including:

- Invasion of the axial skeleton or skull base or skull base foramina
 - Node positive disease
 - Tumor greater than 2cm with any 1 additional feature, including:
 - Recurrent Disease
 - Perineural invasion
 - Lymphovascular space invasion
 - Poorly differentiated histology
 - Positive Margins
 - Satellitosis or in-transit metastases
- Note: Not all patients with tumors >2cm with one additional risk factor may be ideal candidates for this study, such as patients with only focal perineural invasion without other adverse features. Clinical judgment should be used by the investigator in carefully selecting patients believed to be at significant risk of recurrence with radiation alone.
- 3) Patients are required to have CT neck and chest or PET/CT and have no documented evidence of distant metastases
 - 4) Patients must not have a history of the following immunosuppressive conditions: bone marrow transplantation and/or organ transplants and/or chronic rheumatic conditions that require active immunosuppressive therapy. Patients with a history of chronic lymphoid or leukemic malignancies which are not under active therapy (no active therapy within the last 3 months) will be eligible. Patients with chronic lymphoid or leukemic malignancies are eligible with or without active disease as long as they have not had treatment within the past three months.
 - 5) Patients may not have had prior therapy with a checkpoint inhibitor (e.g. anti-CTLA-4, anti-PD-1 or anti-PD-L1 therapy);
 - 6) Patients may not have had prior radiotherapy (>30Gy) to the area requiring treatment that would result in any overlap of tissue in both fields
 - 7) Patients may have received chemotherapy or radiation for a previous, curatively treated malignancy provided at least 2 years have elapsed and there is no current evidence of disease (patients with previous or concurrent additional skin cancers will be eligible). Patients with chronic lymphoid or leukemic malignancies are eligible with or without active disease as long as they have not had treatment within the past three months.
 - 8) Eastern Cooperative Oncology Group (ECOG) Performance Status 0-1

- 9) Age \geq 18
- 10) Female subject of childbearing potential should have a negative urine or serum pregnancy within 72 hours prior to receiving the first dose of study medication. If the urine test is positive or cannot be confirmed as negative, a serum pregnancy test will be required.
- 11) Female subjects of childbearing potential should be willing to use 2 methods of birth control or be surgically sterile, or abstain from heterosexual activity for the course of the study through 120 days after the last dose of study medication (Reference Section 5.7.2). Subjects of childbearing potential are those who have not been surgically sterilized or have not been free from menses for > 1 year.
- 12) Male subjects should agree to use an adequate method of contraception starting with the first dose of study therapy through 120 days after the last dose of study therapy.
- 13) Patients must have adequate laboratory values as per Table 1.

Table 1 Adequate Organ Function Laboratory Values

System	Laboratory Value
Hematological	
Absolute neutrophil count (ANC)	$\geq 1,500$ /mcL
Platelets	$\geq 100,000$ / mcL
Hemoglobin	≥ 9 g/dL or ≥ 5.6 mmol/L without transfusion or EPO dependency (within 7 days of assessment)
Renal	
Serum creatinine OR Measured or calculated ^a creatinine clearance (GFR can also be used in place of creatinine or CrCl)	≤ 1.5 X upper limit of normal (ULN) OR ≥ 60 mL/min for subject with creatinine levels > 1.5 X institutional ULN
Hepatic	
Serum total bilirubin	≤ 1.5 X ULN OR Direct bilirubin \leq ULN for subjects with total bilirubin levels > 1.5 ULN
AST (SGOT) and ALT (SGPT)	≤ 2.5 X ULN OR ≤ 5 X ULN for subjects with liver metastases

Albumin	≥ 2.5 mg/dL
^a Creatinine clearance should be calculated per institutional standard.	

